12.5.2. Provision of Study Results and Information to Investigators

When the clinical study report is completed, the sponsor will provide the major findings of the study to the investigator.

In addition, details of the study drug assignment will be provided to the investigator to enable him/her to review the data to determine the outcome of the study for his/her patient(s).

The sponsor will not routinely inform the investigator or patient the test results, because the information generated from this study will be preliminary in nature, and the significance and scientific validity of the results will be undetermined at such an early stage of research.

12.6. Information Disclosure and Inventions

All information provided by the sponsor and all data and information generated by the study center as part of the study (other than a patient's medical records) is the sole property of the sponsor.

All rights, title, and interests in any inventions, know-how, or other intellectual or industrial property rights which are conceived or reduced to practice by the study center personnel during the course of or as a result of the study are the sole property of the sponsor and are hereby assigned to the sponsor.

If a written contract for the conduct of the study which includes ownership provisions inconsistent with this statement is executed between the sponsor and the study center, that contract's ownership provisions shall apply rather than this statement.

All information provided by the sponsor and all data and information generated by the study center as part of the study (other than a patient's medical records) will be kept by the investigator and other study center personnel. This information and data will not be used by the investigator or other study center personnel for any purpose other than conducting the study.

These restrictions do not apply to:

- Information which becomes publicly available through no fault of the investigator or study center personnel
- Information which is necessary to disclose in confidence to an IEC/IRB solely for the evaluation of the study
- Information which is necessary to disclose in order to provide appropriate medical care to a patient
- Study results which may be published as described in Section [12.2.3](#)

If a written contract for the conduct of the study which includes provisions inconsistent with this statement is executed, that contract's provisions shall apply rather than this statement.

12.7. Joint Investigator/Sponsor Responsibilities

12.7.1. Access to Information for Monitoring

In accordance with ICH GCP guidelines, the study monitor must have direct access to the investigator's source documentation in order to verify the data recorded in the eCRFs for consistency.

The monitor is responsible for routine review of the eCRFs at regular intervals throughout the study to verify adherence to the protocol and the completeness, consistency, and accuracy of the data being entered on them. The monitor should have access to any patient records needed to verify the entries on the eCRFs. The investigator agrees to cooperate with the monitor to ensure that any problems detected in the course of these monitoring visits are resolved.

12.7.2. Access to Information for Auditing or Inspections

Representatives of regulatory authorities or of the sponsor may conduct inspections or audits any time during or after completion of this clinical study. If the investigator is notified of an inspection by a regulatory authority, the investigator agrees to notify the sponsor or its designee immediately. The investigator agrees to provide to representatives of a regulatory agency or the sponsor access to records, facilities, and personnel for the effective conduct of any inspection or audit.

14. APPENDICES

APPENDIX 1. SCHEDULE OF ASSESSMENTS

Appendix 1 Table 1: Schedule of Assessments and Procedures Schedule for Dose Escalation and Dose Expansion Phases

Assessments	Pre-Screening (Dose Expansion only) ¹	Screening ²	Cycle 1 (28 days)				Cycles 2- 5 (28 days)		Cycle 6 and Subsequent Cycles in 1st year (Every 28 days)	Subsequent Cycles in the 2nd year and beyond (Every 28 days)	EOT ³	Safety Follow-up ⁴	Efficacy Follow-Up	Survival Follow-Up ⁵
			1	7	15	22	1	15						
Day of Phase	-84 to -29	-28 to -1	1	7	15	22	1	15	1	1	~7 days after last dose	~30 ± 7 days after last dose	Every 8 weeks	Every ~3 months
Allowed time window				-2 days ⁶	± 2 days	± 2 days	± 2 days ⁶	± 2 days	± 3 days	± 3 days			±7 days	
Pre-screening informed consent	X													
Informed consent		X												
Baseline demographics		X												
Medical and cancer history		X												
Complete Physical examination ⁷		X									X			
Limited physical examination ⁸			X	X	X	X	X	X	X	X				
Vital signs (including weight)		X	X	X	X	X	X	X	X	X	X			
Height		X												
ECOG performance status		X	X				X		X	X	X			
12-lead ECG ⁹		-14 to -1 X									X			
Triplicate ECGs ¹⁰			X		X									
Hematology ¹¹		-14 to -1 days X ¹²	X	X	X	X	X	X	X	X	X			
Clinical chemistry ¹¹		-14 to -1 X ¹²	X	X	X	X	X	X	X	X	X			

Assessments	Pre-Screening (Dose Expansion only) ¹	Screening ²	Cycle 1 (28 days)				Cycles 2- 5 (28 days)		Cycle 6 and Subsequent Cycles in 1st year (Every 28 days)	Subsequent Cycles in the 2nd year and beyond (Every 28 days)	EOT ³	Safety Follow-up ⁴	Efficacy Follow-Up	Survival Follow-Up ⁵
			1	7	15	22	1	15	1	1				
Day of Phase	-84 to -29	-28 to -1	1	7	15	22	1	15	1	1	~7 days after last dose	~30 ± 7 days after last dose	Every 8 weeks	Every ~3 months
Allowed time window				-2 days ⁶	± 2 days	± 2 days	± 2 days ⁶	± 2 days	± 3 days	± 3 days			±7 days	
Coagulation		-14 to -1 X ¹²												
Urinalysis ^{11,13}		-14 to -1 X ¹²												
Serum pregnancy test ¹⁴		-7 to -1 X												
Urine pregnancy test ¹⁵							X		X	X	X			
CT or MRI ¹⁶		X	EVERY 8 WEEKS ± 7 DAYS								X		X	
Tumor antigens ¹⁷		X	EVERY 8 WEEKS ± 7 DAYS								X		X	
HBV/HCV tests ¹⁸		X	As clinically indicated											
TMZ Dosing Dose escalation			Pulsed Dosing (Arm A): Once daily on Days 1 to 7 or Days 1-14 of each 28 day cycle Continuous Dosing (Arm B): Once daily continuously											
TMZ Dosing Dose Expansion			RP2D= 60 mg QD 60 mg QD Days 1-7 of each cycle											
Pamiparib Dosing			60 mg twice daily continuously											
Adverse events		X	X	X	X	X	X	X	X	X	X	X		
Concurrent medications ¹⁹		X	X	X	X	X	X	X	X	X	X	X		
PK assessments ²⁰			X	X	X									
Blood sample collection for biomarkers ²¹		X	X		X						X			
Archival Tumor Tissue or fresh tumor tissue ²²	X		X											
Fresh Tumor Tissues ²³ (Dose Escalation and Dose Expansion Cohorts 1-5;	X		X		X						X			

Assessments	Pre-Screening (Dose Expansion only) ¹	Screening ²	Cycle 1 (28 days)				Cycles 2- 5 (28 days)		Cycle 6 and Subsequent Cycles in 1st year (Every 28 days)	Subsequent Cycles in the 2nd year and beyond (Every 28 days)	EOT ³	Safety Follow-up ⁴	Efficacy Follow-Up	Survival Follow-Up ⁵
			1	7	15	22	1	15	1	1				
Day of Phase	-84 to -29	-28 to -1	1	7	15	22	1	15	1	1	~7 days after last dose	~30 ± 7 days after last dose	Every 8 weeks	Every ~3 months
Allowed time window				-2 days ⁶	± 2 days	± 2 days	± 2 days ⁶	± 2 days	± 3 days	± 3 days			±7 days	
additional consent required)														
Survival Status														X

ECG: electrocardiogram; ECOG: Eastern Cooperative Oncology Group; EOT: end-of-treatment; MRI: magnetic resonance imaging; PK: pharmacokinetic; TMZ: Temozolomide; X: to be performed.

Notes: All assessments must be performed before investigational product administration in each cycle (except as otherwise noted).

- For Dose Expansion Only:** Patients with an unknown germline or somatic *BRCA* mutation or unknown HRD for Expansion Cohorts 1 (ovarian cancer), 2 (TNBC), 3 (mCRPC) and Cohort 6 (multiple indications) will undergo pre-screening for HRD testing for a period of up to 8 weeks prior to eligibility screening (Section 8.1). A separate pre-screening informed consent must be obtained. Any tissues taken during pre-screening period will not be re-collected during the screening period.

For Dose Escalation Only: Cycle 1 encompasses the DLT assessment window, and assessments of Day 1 of Cycle 2 at the end of the DLT assessment window are required for a patient to be DLT-evaluable. Assessments shown for Cycle 3 apply to all subsequent cycles except for MRI that occurs every second cycle (every 8 weeks).
- Screening must occur within 28 days of Day 1. Assessments obtained within 4 days of Day 1 do not have to be repeated on Day 1. Some assessments have a narrower screening window as shown in the table. Patient registration may occur as late as Day 1 prior to any study treatment.
- The EOT visit will occur within 7 days after a patient permanently discontinued study drugs for any of the reasons outlined in Section 8.4. A visit should be scheduled as soon as possible, but the EOT visit may occur later after discussion with the Medical Monitor for specific circumstances, such as prolonged hospitalization. The visit at which CT or MRI showed progressive disease may be used as the EOT visit provided that all required assessments were performed. If routine laboratory tests (e.g., hematology, clinical chemistry) were completed ≤ 7 days before the EOT Visit, these tests do not need to be repeated. The CT/MRI does not have to be repeated if it was performed within 14 days of the EOT visit or at a prior response evaluation that documented progressive disease. ECG does not have to be repeated if it was performed within 14 days of the EOT visit. If the EOT Visit did not occur until 30 days (± 7 days) or later after the last dose of pamiparib and TMZ, the EOT Visit may also be used as the Safety Follow-up Visit.
- All patients who permanently discontinue study drugs will have a safety follow-up approximately 30 days after the last day of study drugs to collect AEs and SAEs that may have occurred after the patient discontinued from the study drugs. If the patient does not require any laboratory assessments, the investigator or his/her designee will contact the patient to collect this information. (Protocol Section 8.5.1).
- Following permanent discontinuation of study drugs and/or Safety Follow-up parts of the study, every effort should be made to follow up with all patients by phone every 3 months for their survival status until patient death (Protocol Section 8.5.3).

6. A window of ± 2 days on Cycle 1 Day 7 and Cycle 2 Day 1 is allowed during **Dose Expansion Only**.
7. Complete physical examination includes the following items: 1) general appearance; 2) head, eyes, ears, nose, and throat; 3) neck; 4) heart; 5) chest (including lungs); 6) abdomen; 7) extremities; 8) skin; 9) lymph nodes; 10) cardio-vascular; 11) neurological status.
8. A limited physical examination should be directed at the evaluation of symptoms or specific safety issues. Changes from baseline abnormalities should be recorded at each subsequent physical examination. New or worsening abnormalities should be recorded as AEs if appropriate.
9. A single 12-lead ECG will be performed during Screening within 14 days of Cycle 1 Day 1 and at the EOT visit.
10. **For Dose Escalation and Dose Expansion Cohorts 1-5 Only:** ECGs will be performed in triplicate within a 5-minute window **prior** to Pamiparib PK assessments on Day -2 or Days 1 and 15. ECGs collected on the days of PK assessment will be performed on a machine provided by the sponsor and will be sent to a central reader. The same machine should be used for each patient whenever possible.
11. Hematology includes hemoglobin, platelet count, white blood cell count, neutrophil count, and lymphocyte count. Chemistry includes albumin, alkaline phosphatase, alanine aminotransferase, aspartate aminotransferase, blood urea nitrogen, chloride, creatinine, glucose, lactate dehydrogenase, phosphate, potassium, sodium, total bilirubin, and total protein.
Urinalysis includes blood, glucose, ketones, protein, red blood cells, and white blood cells.
In the event of clinically significant laboratory results, such as neutropenia (absolute neutrophil count $< 1000/\text{mm}^3$), thrombocytopenia (platelets $< 50,000/\text{mm}^3$), or Grade ≥ 3 clinical chemistry toxicity (per NCI CTCAE v4.03), these assessments will be conducted as frequently as the investigator feels is necessary until toxicity resolves to Grade ≤ 2 .
12. Screening blood and urine tests must be performed within 14 days of Day 1. If they were performed within 4 days of Day 1 they do not need to be repeated on Cycle 1 Day 1.
13. If urine protein is $\geq 2+$ by dipstick, a 24-hour urine for total protein and a random urine for total protein and creatinine will be obtained and evaluated (Section 7.6.3).
14. Only in women of childbearing potential; a serum pregnancy test must be taken ≤ 7 days from Cycle 1, Day 1.
15. For subsequent pregnancy testing on study and at EOT, urine pregnancy tests are allowed. If a urine pregnancy test is positive, a confirmatory serum pregnancy test is required.
16. A computed tomography (CT) or MRI scan of the thorax, abdomen, and pelvis plus other relevant evaluations as appropriate will be performed once every 8 weeks ± 7 days to assess all known disease. A CT/MRI taken within 28 days (Screening Period) of Cycle 1 Day 1 does not need to be re-taken. Patients without PD at the EOT Visit should be followed with tumor assessments every 12 weeks (± 7 days).
17. Blood tumor antigens such as CA-125 for ovarian cancer and PSA for castration-resistant prostate cancer will be tested during screening and every 8 weeks ± 7 days after the first dose of pamiparib in local laboratories. The CA-125 responses must be confirmed and maintained for at least 28 days. Patients can be evaluated according to CA-125 only if they have a pretreatment sample that is at least twice the upper limit of the reference range and within 2 weeks before starting the treatment.
18. Testing will be performed by local laboratory at screening and as clinically indicated and will include HBV/HCV serology (hepatitis B surface antigen, hepatitis B surface antibody, hepatitis B core antibody, and HCV antibody) and viral load assessment (HBV DNA and HCV RNA).
19. Concurrent medications will be collected during screening and on the first day of study. Changes to Concurrent medications will be collected during subsequent clinic visits.
20. Pharmacokinetic (PK) samples will be collected at the following timepoints: For pamiparib: ≤ 30 min before pamiparib and TMZ dosing, 1 (± 15 min), 2 hours (± 30 min), and 4 hours (± 30 min) after pamiparib dose on Cycle 1 Day 1 and Cycle 1 Day 15; For TMZ: on Cycle 1 Day 1 and Day 7 at ≤ 30 min before dosing and 1 hour (± 15 min) after TMZ dose.
21. Blood samples must be collected at screening or on Day 1 for the assessment of germline *BRCA* and/or other mutation analysis (8 ml). In addition, two blood samples (10 mL each) must be collected for plasma markers (e.g., CNA), TMZ treatment, and PARP inhibition **before** study treatment on Day 1 and

Day 15, and at the EOT visit (unless one had been collected within 14 days). Instructions for the processing, storage, and shipping of samples will be provided in the Study Manual.

22. For patients in Expansion Cohorts 1 (ovarian cancer), 2 (TNBC), and 3 (mCRPC) with unknown *BRCA* mutation or HRD status, collection of archival tumor tissue is required during pre-screening to determine eligibility. For patients in Dose escalation and Cohorts 4 and 5, collection of archival tumor tissue for the purpose of biomarker analysis is required, if available and can be collected on screening or Cycle 1 Day 1. For patients in Cohort 6, collection of an archival tumor tissue sample is mandatory for prospective HRD testing to determine eligibility and should be collected during the prescreening period. Specific instructions for tissue collection and shipment are provided in the Study Manual. **Any tissue provided during pre-screening period will not be re-collected during screening stage.**
23. **For patients in Dose escalation, and patients in Dose expansion Cohorts 4 and 5:** a fresh baseline biopsy of a tumor lesion is highly recommended if archival tissue is not available. Written patient consent is required for fresh tumor biopsies.
For patients with unknown mutation or HRD status in Expansion Cohorts 1 (ovarian cancer), 2 (TNBC), and 3 (mCRPC) or patients in Expansion Cohort 6: if archival tumor tissue is not available, a fresh biopsy must be provided for prospective HRD testing at prescreening. Patients will only be required to sign the prescreening consent form. **Any tissue taken during pre-screening period will not be re-collected during screening stage.**
Dose escalation and Dose expansion Cohorts 1-5: An optional biopsy for pharmacodynamics analysis on Cycle 1 Day 1 and, if agreeable, also on Cycle 1 Day 15 is highly recommended. Optional biopsy will also be taken, if agreeable, at the EOT visit for the patients who have confirmed disease progression during the study from accessible tumor sites to obtain samples to explore resistance mechanisms. If feasible, any follow up biopsy should be ideally taken from the same tumor lesion as the baseline biopsy (See Section 7.9.2)

Appendix 1 Table 2: Schedule of Assessments and Procedures for PK Intensive Visit (Days -2 to 1): Only for Approximately 20 Patients - Dose Escalation ONLY

Assessments	Day -2 (± 3 days) ¹							Day -1	Day 1
	Pre-dose	0 h	0.5 h	1 h	2 hr	4 h	6 h	24 h	48 h
Allowed time window			± 5 min	± 15 min	± 30 min	± 30 min	± 30 min	± 2 h	± 2 h
Concurrent medications	X								
Complete Physical examination ²	X								
Limited physical examination ³									X
Vital signs (including weight)	X						X	X	X
ECOG performance status	X								
Hematology	X								
Clinical chemistry	X								
Coagulation	X								
Urinalysis ⁴	X								
Blood sample collection for biomarkers ⁵	X								
Computed tomography or MRI ⁶	X								
Triplicate ECGs ⁷	X			X	X	X	X		
Pamiparib PK assessments ⁸	X		X	X	X	X	X	X	X
Pamiparib Dosing ⁹		X							X
Archival Tumor Tissues ¹⁰	X								
Fresh Tumor Tissues ¹¹ (additional consent required)	X								
Adverse events	X							X	X
TMZ Dosing ¹²									X
TMZ PK assessments ¹³									X

CT: Computerized tomography; ECG: electrocardiogram; ECOG: Eastern Cooperative Oncology Group; MRI: magnetic resonance imaging; PK: pharmacokinetic;

TMZ: Temozolomide; X: to be performed.

Notes: All assessments except for post-dose ECGs and PK samples and biopsies must occur before pamiparib administration. ECGs must occur before PK sampling and biopsies must be performed after all ECGs have been completed on Day -2. For patients enrolled into the PK intensive part of the study, the pre-dose biopsy must occur **after** the patient was approved for enrollment and **before** dosing on Cycle 1 Day -2.

1. Screening must occur within 28 days of Day -2. Assessments obtained within 4 days of Day -2 do not have to be repeated on Day -2. Patient registration may occur as late as Day -2 prior to any study treatment.
2. Complete physical examination includes the following items: 1) general appearance; 2) head, eyes, ears, nose, and throat; 3) neck; 4) heart; 5) chest (including lungs); 6) abdomen; 7) extremities; 8) skin; 9) lymph nodes; 10) cardio-vascular; 11) neurological status.
3. A limited physical examination should be directed at the evaluation of symptoms or specific safety issues. Changes from baseline abnormalities should be recorded at each subsequent physical examination. New or worsening abnormalities should be recorded as AEs if appropriate.
4. If urine protein is $\geq 2+$ by dipstick, a 24-hour urine for total protein and a random urine for total protein and creatinine will be obtained and evaluated (Section 7.6.3).
5. Blood samples will be collected **before** study treatment on Day -2 for the assessment of germline *BRCA* and/or other mutation analysis (8 ml). In addition, two blood samples (10 mL each) must be collected for plasma markers (e.g., CNA), TMZ treatment, and PARP inhibition. Instructions for the processing, storage, and shipping of samples will be provided in the Study Manual.
6. A computed tomography (CT) or MRI scan of the thorax, abdomen, and pelvis plus other relevant evaluations as appropriate will be performed.
7. ECGs will be performed in triplicate on Day -2 within a 5-minute window **prior** to pamiparib PK assessments. ECGs for each patient should be obtained from a calibrated machine provided for the study and the same machine must be used for all ECG assessments on Day -2. Triplicate ECGs will be sent to a central reader.
8. Pamiparib PK samples will be collected at the following timepoints: For pamiparib: ≤ 30 min before dosing on Day -2 and post-dose at 30 min (± 5 min); 1 hour (± 15 min); 2 hours (± 30 min), 4 hours (± 30 min), and 6 hours (± 30 min), 24 hours (± 2 h) on Day -1, and 48 hours (± 2 h) on Day 1.
9. Pamiparib dosing must occur after the collection of the 48-hour post-dose PK sample on Day 1.
10. Collection of archival tumor tissue for purpose of biomarker analysis is highly recommended. Specific instructions for tissue collection and shipment are provided in the Study Manual.
11. In the absence of archival tumor tissues, a fresh baseline biopsy of a tumor lesion is highly recommended. **Any tissues taken during pre-screening period will not be re-collected during baseline.** An optional biopsy for biomarker analysis after treatment on Cycle 1 and if agreeable, also on Cycle 1 Day 15, and EOT is highly recommended. Optional biopsy will also be taken at the EOT visit for the patients who have confirmed disease progression during the study from accessible tumor sites to obtain samples to explore resistance mechanisms. If feasible, any follow up biopsy should be ideally taken from the same tumor lesion as the baseline biopsy. Written patient consent is required for fresh tumor biopsies. Fresh biopsies should be limited to readily accessible tumor lesions (e.g., skin, peripheral lymph nodes, lung, liver or internal lymph node metastases which can be readily accessed using CT guidance). If performed, a tissue cylinder should be obtained that has proper size for histological examination and biomarker analysis.
12. TMZ dosing must occur after the collection of the 48-hour post-dose PK sample on Day 1.
13. TMZ PK samples will be collected at the following timepoints: pre-dose (within 30 min prior to dose) and 1 hour (± 15 min) post dose.

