8.4. End-of-Treatment Visit

Patients who discontinue from study drug for any of the reasons listed below will undergo an EOT visit within 7 days of discontinuation of all study drugs. If routine laboratory tests (e.g., hematology, clinical chemistry) were completed ≤ 7 days before the EOT Visit, these tests do not need to be repeated.

However, the EOT visit may occur later than 7 days after discussion with the Medical Monitor for specific circumstances, such as prolonged hospitalization. If the EOT Visit did not occur until 30 days (± 7 days) or later after the last dose of pamiparib and TMZ, the EOT Visit may also be used as the Safety Follow-up Visit.

Patients with a required EOT visit may discontinue study drug for any of the following reasons:

- Disease progression

- Investigator decision
- Adverse event(s)
- Pregnancy
- Patient withdrew consent for study drug
 - Patients may voluntarily withdraw consent from study drug at any time
 - Patients may continue to participate in the Follow-up Phase, if the patient withdraws consent from the Treatment Phase
- Start of other anticancer therapy
- Patient noncompliance
 - Study site staff should first counsel patients who are significantly noncompliant (e.g., missing 2 treatment cycles) on the importance of study drug compliance and drug accountability. The investigator may, in consultation with the medical monitor, discontinue patients from treatment who are consistently noncompliant

The reason for discontinuation from study drug will be recorded on the eCRF.

All the assessments performed for the EOT visit are listed in the Schedule of Assessments ([Appendix 1 Table 1](#)).

The visit at which the assessment showed progressive disease may be used as the EOT visit provided that all required assessments were performed. A CT does not have to be repeated at the EOT visit if it was performed within 14 days of the visit or at a prior response evaluation that documented progressive disease. ECG does not have to be repeated if it was performed within 14 days of the EOT visit.

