8.5. Follow-up Assessments

8.5.1. Safety Follow-Up

All patients who discontinue study drugs will have a safety follow-up approximately 30 days after the last day of study drugs to collect AEs and SAEs that may have occurred after the patient discontinued from the study drugs as well as concomitant medications. The investigator or his/her designee will also contact the patient to collect AE and SAE information as well as any new anticancer therapy given after the last day of study drugs. A laboratory assessment is only required if the patient had an ongoing laboratory abnormality at the previous visit that the investigator considered to be related to study drugs.

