10.4. Timing, Frequency, and Method of Capturing Adverse Events and Serious Adverse Events

10.4.1. Adverse Event Reporting Period

After informed consent has been signed but prior to the administration of the study drug, only SAEs should be reported.

After initiation of study drug, all AEs and SAEs, regardless of relationship to study drug, will be reported until 30 days after the last study treatment or initiation of new anticancer therapy.

After a patient is discontinued from the study, investigators are not obligated to actively seek AEs or SAEs from the former patients. After this period, the investigator should report any SAEs that are believed to be related to prior study drug treatment.

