11.3.3. Adverse Events

The AE verbatim descriptions (investigator terms from the eCRF) will be classified into standardized medical terminology using MedDRA®. Adverse events will be coded to MedDRA® (Version 19.0 or higher) lower level term closest to the verbatim term. The linked MedDRA® preferred term (PT) and primary system organ class (SOC) are also captured in the database.

A treatment emergent adverse event (TEAE) is defined as an AE that had an onset date on or after the first dose of study drugs up to 30 days following study drug discontinuation or was worsening in severity from baseline (pretreatment). Only those AEs that were treatment emergent will be included in summary tables. All AEs, treatment emergent or otherwise, will be presented in patient data listings.

The incidence of TEAEs will be reported as the number (percentage) of patients with TEAEs by SOC and PT. A patient will be counted only once by the highest grade according to NCI [CTCAE v.4.03](#) within an SOC and PT, even if the patient experienced more than one TEAE within a specific SOC and PT. The number (percentage) of patients with TEAEs will also be summarized by relationship to the study drug. Treatment-related AEs include those events considered by the investigator to be possibly or probably related to study drug or with missing assessment of the causal relationship. Serious adverse events, deaths, TEAE with Grade 3 or above, related TEAE and TEAEs that led to treatment discontinuation, dose reduction or dose delay will be summarized.

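### The safety follow-up window allows the last scheduled adverse-event contact up to 7 days before the 30-day reporting and treatment-emergent period ends

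*Protocol*

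**What the plan says.** In this note, Day n means n days after the last dose of study drug.

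- **Timing of the contact.** The Safety Follow-up column of Protocol Appendix 1 Table 1 is set at about "30 ± 7 days after last dose". Section 8.5.1 gives roughly 30 days and no tolerance. Footnote 4 lets it be a contact rather than a visit when no laboratory test is needed.
- **Where AEs are scheduled.** The adverse-event row of that table is marked up to and including Safety Follow-up. The Efficacy and Survival Follow-Up columns have no AE mark.
- **Reporting period.** Protocol Section 10.4.1 says that all AEs and SAEs after the first dose "will be reported until 30 days after the last study treatment or initiation of new anticancer therapy". Section 7.4 says the same.
- **Counting period.** Protocol Section 11.3.3 counts events with onset "on or after the first dose of study drugs up to 30 days following study drug discontinuation". SAP Section 6.2.1 runs the period to 30 days after the last pamiparib dose or to new anticancer therapy.
- **Substitution.** Protocol Section 8.4 and footnote 3 of the table provide: "If the EOT Visit did not occur until 30 days (± 7 days) or later after the last dose of pamiparib and TMZ", then "the EOT Visit may also be used as the Safety Follow-up Visit".

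**The concern.** Incidence, nature and severity of AEs is a primary endpoint (Protocol Section 3.1, SAP Section 4.1). The safety follow-up is the only contact after the end-of-treatment visit that is dedicated to collecting AEs, yet its symmetric tolerance lets it take place before the period that it serves has closed. A site that calls on Day 23 has complied with the schedule, and nothing scheduled then asks the patient about Days 24-30. The substitution rule repeats the tolerance, so an end-of-treatment visit on Day 23 can be the last AE contact. Any loss can only lower the counts, because an event that is not elicited is not recorded.

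**Working it through.** The plan states no figure for this point, so there is none to reproduce. The check is date arithmetic.

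**Inputs.** Nominal contact Day 30 and tolerance 7 days (Appendix 1 Table 1); period end Day 30 (Protocol Sections 7.4, 10.4.1 and 11.3.3; SAP Section 6.2.1).

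**Window.** Earliest contact 30 − 7 = Day 23; latest 30 + 7 = Day 37. Permitted days: 37 − 23 + 1 = 15. Days 23-29 (7 of 15, 47%) fall before Day 30 and Days 30-37 (8 of 15) do not.

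**Gap without a scheduled contact.** For a contact on Day d, gap = max(0, 30 − d).

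- Worst case, d = 23: 7 days, and 7/30 = 23% of the period.
- d = 30 or later: 0 days.
- Even spread over the 15 permitted days (assumption): (7+6+5+4+3+2+1)/15 = 28/15 = 1.9 days, and 1.9/30 = 6% of the period. Among early contacts alone the mean is 28/7 = 4 days, but that is not the average over all patients.

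The documents give no distribution of contact dates, so the average gap could lie anywhere from 0 to 7 days. Section 8.5.1 aims at about Day 30, which makes an average near 7 unlikely.

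**Which last dose.** The contact is timed from the last study drug, and so is the protocol's reporting period, so the gap under that rule is up to 7 days whichever drug stops last. The SAP's period runs from the last pamiparib dose. If pamiparib stops L days before TMZ, the largest gap under the SAP is max(0, 7 − L): 7 days at L = 0, and 0 days at L = 7 or more. In expansion, pamiparib is continuous and TMZ is given on Days 1-7 of each cycle (Appendix 1 Table 1), so pamiparib will usually be the last drug taken and the 7-day bound usually applies.

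**Earlier closure.** If new anticancer therapy starts on Day t before Day 30, the gap becomes max(0, t − d).

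**What later contacts could recover:**

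| Event starting after an early contact, by Day 30 | Route to the database |
|---|---|
| Related SAE | Reportable by date. If it starts after the period, it is still reported (Protocol Section 10.4.1) and counted (SAP Sections 6.2.1 and 6.4.3) |
| Non-serious AE or unrelated SAE, patient without progression | Reportable by date. The 8-weekly efficacy follow-up (Section 8.5.2) is a site visit at which safety assessments apply (Section 7.4) |
| Non-serious AE or unrelated SAE, patient with progression | Reportable by date, but no later clinic visit is scheduled. The roughly 3-monthly survival contact covers survival and further therapy (Section 8.5.3) |

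The last row is where scheduled elicitation is missing.

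**The case against.** The strongest reply is that reporting is tied to a date and not to a visit. No section closes AE collection at the safety follow-up, so an event on Day 27 must be reported and falls inside the counting window whether the contact was on Day 23 or Day 33. A reader might infer that late events are missed; the documents do not support that. Related SAEs are covered beyond the period, AEs already open are followed further (Sections 7.4 and 10.1.1.3), and patients without progression keep returning. A late end-of-treatment visit is also an exception, to be discussed with the Medical Monitor for circumstances such as a long hospital stay (Section 8.4).

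All of this stands, and it narrows the point to new non-serious AEs and unrelated SAEs. It does not remove the point. A duty to report does not bring an event to the site's notice. Section 10.4.2 relies on asking patients what has happened since the last visit, and after an early contact a patient who has progressed has no scheduled occasion for that question.

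Three further inferences are tempting and also unsupported:

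- **Every treated patient, up to 250, is affected.** Contacts on Days 30-37 leave no gap, and neither does a period already closed by new therapy.
- **Late cytopenias are the events lost.** Nothing places them in Days 24-30. The safety follow-up requires a laboratory test only for an ongoing abnormality judged related to study drug (Section 8.5.1), so a later contact adds no blood count.
- **Cohorts or sites are biased by different amounts.** The documents hold no data on contact timing.

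**Conclusion.** The mismatch is real and small. The schedule permits the last dedicated AE contact up to 7 days before the reporting and treatment-emergent period ends, and permits a delayed end-of-treatment visit to take its place equally early. The consequence is possible under-ascertainment of two kinds of event, mainly after progression, and not a demonstrated loss. The 23% figure is a bound for one patient contacted on Day 23. The 6% figure rests on the even-spread assumption and on no earlier start of new therapy. Both measure days without a scheduled contact, not events lost, which cannot be estimated from the documents. No stated figure in the plan changes. The case for acting is that the remedy is cheap and the endpoint is primary.

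**What to change.** In Protocol Appendix 1 Table 1, footnote 4 and Section 8.5.1, set the safety follow-up contact at 30 days +7, that is Days 30-37 after the last dose of study drug. In Section 8.4 and footnote 3, let the end-of-treatment visit double as the safety follow-up only when it takes place on or after Day 30. Where contact is made earlier because new anticancer therapy is starting, the existing cut-off at new therapy applies and nothing further is needed.

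The largest gap then becomes max(0, 30 − 30) = 0 days. Timing from the last study drug also covers the SAP's period, because the last pamiparib dose cannot be later than the last dose of study drug.

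The cost is a wording change in the protocol. No visit or test is added. Some contacts move up to a week later, and an end-of-treatment visit on Days 23-29 would no longer spare the patient a separate safety contact.
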